Pomalidomide: This third generation IMiD was approved for the treatment of relapsed/refractory myeloma in 2013 for patients who had received at least two prior regimens including lenalidomide and bortezomib. This agent has only been evaluated in the previously treated setting. In one phase II study, the combination of pomalidomide and dexamethasone where the pomalidomide was dosed at 2 mg daily had a 63% overall response rate including 40% ORR in lenalidomide-refractory patients and 37% ORR in thalidomide-refractory patients(17). In another study which included only lenalidomide-refractory patients, the overall response rate was 47%(18). An alternative dosing strategy of 4 mg daily for 21 out of 28 days was also explored and the ORR was 35–42% (19, 20).

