4.0 Test Schedule

Tests and procedures	Active Monitoring Phase					
	Prior to registration		Prior to Day 1 Cycle 1	Prior to Day 1 Cycle 2	Prior to Day 1 Cycles 3-6	End of Treatment
	≤28 days	≤14 days				
Window				±3 days	±3 days	±7 days
Complete Medical History		X				
Physical exam, Wt, PS		X	X ³	X	X	X
Adverse event assessment		X		X	X	X
Pregnancy test ¹		X				
Height		X				
Hematology group: CBC with 5-part differential		X	X ³	X	X	X
Chemistry group to include serum creatinine, calcium, T.Bili, D. bili, AST, and ALT		X	X ³	X	X	X
LDH, Beta-2-microglobulin, Plasma cell assessment		X	X ³			
PT/PTT/INR		X				
TSH		X				
Electrophoresis of serum and urine		X	X ^{3,5}	X ⁵	X ⁵	X ⁵
Immunofixation or mass fixation of serum and urine		X		X ⁷	X ⁷	X ⁷
Affected Serum Immunoglobulin ²		X	X ³	X	X	X
Serum Immunoglobulin free light chain		X	X ³	X	X	X
WBLDCT ³ or PET/CT	X			X ³	X ³	
Bone marrow aspirate and biopsy	X					
Patient Medication Diary (Appendix II)			X	X	X	
Research bone marrow sample ^R	X			X ⁶		X ⁴
Research blood sample ^R	X			X ⁶		X ⁴

Cycle 1 = 21

Cycles 2-6 = 28 days

Footnotes on following page:

1. For women of childbearing potential only. Must be done ≤ 7 days prior to registration. If the urine test is positive or cannot be confirmed as negative, a serum pregnancy test will be required
2. Affected immunoglobulin refers to the baseline M-protein type, that is, IgG, IgA, or IgD. Not applicable if patient “non-secretory” or if patient has no heavy chain, i.e. light chain myeloma. Affected immunoglobulin is required after baseline only if it used for disease monitoring instead of SPEP (e.g. IgA myeloma).
3. Baseline then only if clinically indicated.
4. Optional BM sample submission for patients who discontinue treatment due to disease progression or relapse, intolerable AEs, patient refusal, subsequent treatment for myeloma.
5. Urine Electrophoresis required only if used to assess disease response
6. Bone marrow aspirate done at the end of Cycle 1 (prior to cycle 2) will be paid for by research.
7. Immunofixation (IF) only needed in absence of M-Spike to document CR or SCR

R Collected as part of the IRB# 521-93, IRB# 14-009163 and/or IRB# 919-04

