7.0 Protocol Treatment

7.1 Treatment Schedule

Cohort A and B Cycle 1

Treatment medication table. Patient may receive Lenalidomide OR Lenalidomide + Dexamethasone.

Agent	Dose Level	Route	Day	Re Rx
Lenalidomide	25 mg*	Oral	Cycle 1: Day 1-14	Cycle 1: 21 days
Dexamethasone	40 mg**	Oral	Cycle 1: Day 1 ,8, ,15	Cycle 1: 21 days

Cycle 1 length = 21 days

* Starting dose will be determined as per the creatine clearance below (see 7.12)

**The dose of dexamethasone used can be determined by the treating physician and omitted if needed.

Cohort C and D Cycle 1

Treatment medication table. Patient may receive Lenalidomide + Dexamethasone OR Pomalidomide + Dexamethasone.

Agent	Dose Level	Route	Day	ReRx
Lenalidomide	25 mg*	Oral	Cycle 1: Day 1-14	Cycle 1: 21 days
Pomalidomide	4 mg	Oral	Cycle 1: Day 1-21	Cycle 1: 21 days
Dexamethasone	40 mg**	Oral	Cycle 1: Day 1 ,8, ,15	Cycle 1: 21 days

Cycle 1 length = 21 days

* Starting dose will be determined as per the creatinine clearance below (see 7.12)

** The dose of dexamethasone used can be determined by the treating physician and omitted if needed.

Cohort A and B Cycles 2-6

Treatment Medication Table. Patient may receive Lenalidomide based regimens.

Agent	Dose Level	Route	Day	Re Rx
Lenalidomide	25 mg*	Oral	Cycle 2-6: Day 1-21	Cycles 2-6: 28 days
Dexamethasone	40 mg**	Oral	Cycle 2-6: Day 1 ,8, ,15, 22	Cycles 2-6: 28 days

Note: Standard of care agents can be added for cycles 2-6 as long as the regimen contains lenalidomide

Cycles 2-6 length = 28 days

* Any dose-adjustments will be determined as per the creatine clearance below (see 7.12).

** The dose of dexamethasone used can be determined by the treating physician and omitted if needed.

Cohort C and D Cycles 2-6

Treatment medication table. Patient may receive Lenalidomide based regimen OR Pomalidomide based regimen.

Agent	Dose Level	Route	Day	ReRx
Lenalidomide	25 mg*	Oral	Cycles 2-6: Day 1-21	Cycles 2-6: 28 days
Pomalidomide	4 mg	Oral	Cycles 2-6: Day 1-21	Cycles 2-6: 28 days
Dexamethasone	40 mg**	Oral	Cycle 2-6: Day 1,8,15,22	Cycles 2-6: 28 days

Note: Standard of care agents can be added for cycles 2-6 as long as the regimen contains lenalidomide or pomalidomide

Cycles 2-6 length = 28 days

* Any dose-adjustments will be determined as per the creatinine clearance below (see 7.12).

** The dose of dexamethasone used can be determined by the treating physician and omitted if needed.

7.12

Creatinine Clearance (CrCl)	Lenalidomide Dose

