8.4 Pomalidomide–Related Treatment Modification Guidelines for Adverse Events

8.41 Pomalidomide Dose Modifications

Pomalidomide (Cycle 1: Day 1-21 Cycle 2-6: Day 1-21)	
Dose Level	
Starting dose	4 mg
-1	3 mg
-2	2 mg
-3	1 mg
-4	Discontinue

→ → Use the NCI Common Terminology Criteria for Adverse Events (CTCAE) version 5.0*
unless otherwise specified ← ←

CTCAE System/Organ/Class (SOC)	ADVERSE EVENT	AGENT	ACTION**
Investigations	Neutrophil count decreased If ANC $<1.0 \times 10^9/L$ or ANC $>1.0 \times 10^9/L$ (up to LLN) with fever (temperature $>38.5^{\circ}C$)	Pomalidomide	Omit pomalidomide dose. Follow CBC weekly. If neutropenia has resolved to \leq Grade 2 prior to Day 21 and fever has resolved, restart pomalidomide at next lower dose level and continue through Day 21 of a 28-day cycle. If febrile neutropenia is the only toxicity for which a dose reduction is required, G-CSF may be used and the pomalidomide dose maintained.

CTCAE System/Organ/Class (SOC)	ADVERSE EVENT	AGENT	ACTION**
Investigations	Platelet count decreased If platelet count $<30 \times 10^9/L$	Pomalidomide	Omit pomalidomide dose Follow CBC weekly Hold anticoagulation/antiplatelet therapy until platelets $\geq 50,000/mm^3$ If platelet count resolves to \leq Grade 2 prior to Day 21, restart pomalidomide at next lower dose level and continue through Day 21 of each cycle
Skin and subcutaneous tissue disorders	Rash maculopapular Grade 2 or 3	Pomalidomide	Omit pomalidomide dose; follow weekly If the AE resolves to \leq Grade 1 prior to Day 21, restart pomalidomide at next lower dose level and continue through Day 21 of each cycle
	Grade 3-4 Stevens –Johnson Syndrome	Pomalidomide	Discontinue pomalidomide and remove patient from all study treatment
	\geq Grade 3 Erythema multiforme	Pomalidomide	Discontinue pomalidomide and remove patient from all study treatment
	Erythroderma \leq Grade 3	Pomalidomide	Omit pomalidomide dose; follow weekly If the AE resolves to \leq Grade 1 prior to Day 21, restart pomalidomide at next lower dose level and continue through Day 21 of the 28-day cycle
	Rash, maculo-papular Rash, acneiform Grade 4	Pomalidomide	Discontinue pomalidomide and remove patient from all study treatment
Nervous system disorders	Peripheral sensory neuropathy Grade 3	Pomalidomide	Omit pomalidomide dose and follow at least weekly. If the AE resolves to \leq Grade 1 prior to Day 21, restart pomalidomide at next lower dose level and continue through Day 21

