- 15.261 Cytopenias are common (neutropenia most common). Monitor CBC closely and instruct patient to report any signs/symptoms of infection or unusual bruising or bleeding to the study team.
- 15.262 Thrombotic events have been reported. Anticoagulation prophylaxis may be recommended. Instruct patients to report any problems with bleeding, extremity pain or swelling, or shortness of breath to the study team immediately.
- 15.263 Patients may experience cough, URI, pneumonia, or sinusitis. Instruct patients to report respiratory symptoms to the study team.
- 15.264 Gastrointestinal side effects consisting of diarrhea, constipation, stomatitis, nausea, decreased appetite, and abdominal pain have been seen. Treat symptomatically and monitor for effectiveness.
- 15.265 Drug should be taken without food (at least 2 hours before or 2 hours after a meal). Do not open or crush capsules.
- 15.266 Patients may experience myalgias and muscle spasms. Treat symptomatically and monitor for effectiveness.
- 15.267 Fatigue is common. Instruct patient in energy conserving lifestyle.
- 5.199b Warn patients about the possibility of peripheral neuropathy, headache, confusion, and dizziness.
- 15.199c Patients may experience URI, pneumonia, dyspnea, and cough. Instruct patients to report respiratory symptoms to the study team.
- 15.199d Severe dermatologic reactions have been seen (including urticaria). Instruct patient to report and rash or skin changes to the study team.
- 15.199e All patients must be registered in the POMALYST REMS program. See protocol for more details.
- 15.99f Monitor creatinine, as patients may experience elevated creatinine levels, with rare reports of renal failure.

15.199g Rare reports of GI bleeding have been seen. Instruct patient to report any hematochezia, or melena to the study team immediately.

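### Cohorts C and D: cycle-1 pomalidomide runs straight into cycle 2, giving up to 42 consecutive IMiD days with one scheduled CBC; a CBC at about cycle 2 day 15 is a cheap safeguard

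*Combined protocol and SAP*

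**What the plan says.** **Dosing.** In section 7.1, the cohort C and D table for cycle 1 gives pomalidomide 4 mg as "Cycle 1: Day 1-21", with a cycle length of 21 days. Cycles 2-6 last 28 days, with either IMiD on days 1-21. For cycles 2-6 the table says "Patient may receive Lenalidomide based regimen OR Pomalidomide based regimen", and a note adds "Standard of care agents can be added for cycles 2-6 as long as the regimen contains lenalidomide or pomalidomide". The header of the dose table in 8.41 repeats the days: "Pomalidomide (Cycle 1: Day 1-21 Cycle 2-6: Day 1-21". Lenalidomide in cycle 1 is given on days 1-14 only.

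**Cited evidence.** Section 1.1 describes a 2 mg daily regimen and, for 4 mg, only this: "An alternative dosing strategy of 4 mg daily for 21 out of 28 days was also explored".

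**Monitoring.** In section 4.0, the row "Hematology group: CBC with 5-part differential" has entries before registration, before cycle 1 day 1 (baseline), before cycle 2 day 1 (±3 days), before day 1 of cycles 3-6 (±3 days) and at end of treatment. Section 8.41 omits pomalidomide at ANC below 1.0 x 10^9/L or platelets below 30 x 10^9/L and then asks for weekly counts. Its neutropenia and erythroderma rows both refer to a 28-day cycle. Item 15.261 says "Cytopenias are common (neutropenia most common). Monitor CBC closely", without an interval.

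**The concern.** Cycle 1 has no pomalidomide-free day, so its last dose and the first IMiD dose of cycle 2 fall on adjacent days. This differs from the only 4 mg schedule the protocol cites, from its own later cycles, and from lenalidomide in the same cycle, which has days 15-21 off. No other section puts a rest back, and no rationale for continuous 4 mg dosing is given.

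What is at stake is hematologic safety in the second half of the run. The omit rules in 8.41 act only if a count is taken, and the weekly counts there start only once a cytopenia has been found. In the same weeks other agents may be added (7.1) and care may pass to a local physician (7.2). That handover calls for a list of follow-up tests, but the protocol supplies no CBC interval to put in it.

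**Working it through.** The plan states no 42-day total. It states 21 of 21 days for cycle 1 and 21 of 28 for cycles 2-6, so the check is a day count.

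**1. Calendar as written.** Cycle 1 is days 1-21, so cycle 2 starts on day 21 + 1 = 22. Later cycles start every 28 days: 50, 78, 106, 134.
- Cycle 1 pomalidomide: days 1-21.
- Cycle 2 IMiD: days 22 to 22 + 20 = 42.
- Longest run: 21 + 21 = 42 days. First rest: days 43-49.
- If cycle 2 starts even one day late, the longest run is 21 days.

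**2. Comparison with 21 of 28 from the start** (cycle 2 on day 29). Doses to date at 4 mg:

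| By day | As written | 21 of 28 | Ratio |
|---|---|---|---|
| 28 | 28 (112 mg) | 21 (84 mg) | 1.33 |
| 42 | 42 (168 mg) | 35 (140 mg) | 1.20 |
| 49 | 42 (168 mg) | 42 (168 mg) | 1.00 |

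Over six cycles both give 6 x 21 = 126 doses (504 mg). The difference is the missing rest week, not the total dose.

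**3. Scheduled CBCs inside the run.** The count before cycle 2 day 1 falls at about day 22. The next is at about day 50, and no earlier than day 46 or 47 with the window, after the run has ended. One scheduled CBC therefore falls inside the run. Dosing days after it: 42 - 22 = 20, or 42 - 19 = 23 if it is taken three days early. A count at the late end of the window (day 25) would leave 17, but it would come after cycle 2 dosing has begun, which the column heading does not suggest.

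**4. Is the 20-day interval peculiar to the run?** No. In cycle 3 the CBC is at day 50 and dosing ends on day 70, so 70 - 50 = 20. What differs is what comes before: a rest on days 43-49 for cycle 3, but 21 unbroken dosing days for cycle 2.

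**5. Effect of one added CBC.** Cycle 2 day 15 is study day 22 + 14 = 36. The 20 days after the day-22 count split into days 23-35 (13 days), day 36 itself, and days 37-42 (6 days). The longest stretch falls from 20 to 13.

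**6. Starting margin.** The entry floor in 3.17 is ANC 1000/mm3 = 1.0 x 10^9/L, level with the omit threshold in 8.41. This holds under any schedule, so it adds weight to monitoring in general and not to the run specifically.

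**7. Patients.** Maximum accrual in cohorts C and D (16.22) is 63 + 63 = 126 of 190. The share who take pomalidomide in cycle 1 and an IMiD in cycle 2 without delay is not given. If it were 25% or 50%, about 32 or 63 patients would be affected.

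**The case against.** The strongest reply accepts the count and disputes its consequence.

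- **The CBC interval is not special.** About 20 dosing days without a scheduled count occur in every later cycle, and a rest week would not change that: doses on days 29-49 after a count before day 29 again leave 20. This stands. It is why the remedy should be a CBC and not a rest week.
- **Other safeguards exist.** Section 8.0 refers adverse-event management to the prescribing information, which is not reproduced. Section 8.41 has omit rules, weekly counts after an event, and growth-factor support: "If febrile neutropenia is the only toxicity for which a dose reduction is required, G-CSF may be used and the pomalidomide dose maintained". Blood counts are graded at each evaluation (10.61), and grade 3-4 events are reported routinely whatever their cause (10.622). Section 16.33 provides at least twice-yearly review and lets the team suspend accrual before a rule is crossed. These stand as partial safeguards, but none schedules a CBC in cycle 2.
- **Harm is not shown.** Exposure evens out by day 49, no cytopenia rate is given for either schedule, and section 1.1 also cites 2 mg daily with no rest stated. This stands, and it limits how strongly the point can be put.

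A reader might infer that hematologic toxicity would go unnoticed, because 10.32 exempts grade 4 cytopenias from expedited reporting and the 16.33 stopping rule counts only non-hematologic events. The documents do not support that. The exemption lapses on hospitalization, febrile neutropenia is not on its list, and routine reporting and periodic review continue.

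**Conclusion.** The point holds as a low-cost safety improvement. Up to 42 consecutive IMiD days follow from the text, against 21 in the cited 4 mg schedule and in cycles 2-6, with one scheduled CBC inside the run and about 20 dosing days after it. This assumes pomalidomide in cycle 1, an IMiD from study day 22, and no omitted dose. The ceiling is 126 patients; the actual number is unknown.

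Three stronger readings are tempting but unsupported. The first is that the schedule is a drafting error: 7.1 and 8.41 give the same days, so it may be intended, although the 28-day wording in 8.41 does not fit a 21-day cycle 1. The second is that patients receive more drug: they do so only until day 49. The third is that the primary result is compromised: response is assessed after cycle 1, before the second half of the run, and is unaffected. Nor do the documents show how much cytopenia risk the missing rest adds.

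**What to change.** 1. In section 4.0, add a CBC at about cycle 2 day 15 (study day 36) for every patient who takes pomalidomide or lenalidomide in cycle 2 after pomalidomide in cycle 1.
2. In 8.41, reword the 28-day references in the neutropenia and erythroderma rows so that they also fit the 21-day cycle 1.
3. Have the sponsor confirm that continuous dosing across cycles 1 and 2 is intended.

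**Cost:** one routine CBC per affected patient (at most 126), one calendar row and a wording change. Dosing, endpoint timing and sample size do not change.

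**If continuous dosing is not intended,** a rest on days 22-28 is an option, but a debatable one. Cycle 2 and any added agents would start on day 29 instead of day 22, with no IMiD that week. Six cycles would take 6 x 28 = 168 days instead of 21 + 5 x 28 = 161. If response and research marrow stayed at day 21, pomalidomide patients would be assessed before their cycle 1 ended and lenalidomide patients at its end. Section 16.311, footnote 6 of section 4.0 and section 19.2 would then need amending so that their references to completing or ending cycle 1 match a day-21 assessment. The cycle 2 monitoring interval would still be about 20 days unless a CBC were added as well.

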3.13 Measurable disease as defined in section 11.0

3.14 Provide written informed consent.

3.15 Patient must be considered for treatment with an IMiD containing regimen.

3.16 ECOG Performance Status (PS) 0, 1, 2 or 3 (Appendix I).

3.17 The following laboratory values obtained \leq 14 days prior to registration:

- Hemoglobin \geq 7.0 g/dL
- Absolute neutrophil count (ANC) \geq 1000/mm³
- Platelet count \geq 50,000/mm³

- Total bilirubin $\leq 1.5 \times$ upper limit of normal (ULN) unless due to Gilbert's syndrome, in which case the direct bilirubin must be $\leq 1.5 \times$ ULN.
- Alanine aminotransferase (ALT) and aspartate transaminase (AST) $\leq 3 \times$ ULN ($\leq 5 \times$ ULN for patients with liver involvement)
- PT/INR/aPTT $\leq 1.5 \times$ ULN OR if patient is receiving anticoagulant therapy and INR or aPTT is within target range of therapy
- Calculated creatinine clearance ≥ 45 ml/min using the Cockcroft-Gault formula below:

Cockcroft-Gault Equation:

$$\text{Creatinine clearance for males} = \frac{(140 - \text{age})(\text{weight in kg})}{(72)(\text{serum creatinine in mg/dL})}$$

$$\text{Creatinine clearance for females} = \frac{(140 - \text{age})(\text{weight in kg})(0.85)}{(72)(\text{serum creatinine in mg/dL})}$$

3.18 Negative pregnancy test done ≤ 7 days prior to registration, for persons of childbearing potential only.
NOTE: If the urine test is positive or cannot be confirmed as negative, a serum pregnancy test will be required.

3.19a Willing to return to enrolling institution for follow-up (during the Active Monitoring Phase of the study).

3.19b Willingness to provide mandatory blood and bone marrow specimens for correlative research (see Section 14.0).

3.19c Willing to follow the requirements of the Pomalyst® REMS program

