CrCl >60 ml/minute	25 mg No adjustment required
CrCl 30-60 ml/minute	10 mg once daily (may increase to 15 mg once daily after 2 cycles if nonresponsive but tolerating treatment)
CrCl <30 ml/minute (non-dialysis dependent)	15 mg every 48 hours

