The serum free light chain (FLC) assay is of particular use in monitoring response to therapy in patients who have oligo-secretory or non-secretory disease and **should be used in assessing response only if the baseline serum and/or urine M proteins are not “measurable” as above, and the baseline level of the involved FLC is “measurable.”** When using this assay, it is important to note that the FLC levels vary considerably with changes in renal function and in patients with renal insufficiency, the levels of both the kappa and lambda may remain elevated, but the ratio normalizes with achievement of CR. Thus, both the level of the involved and the uninvolved FLC isotype (i.e., the involved/uninvolved ratio or involved-uninvolved difference) should be considered in assessing response. ***Patients included on the study on the basis of FLC alone (i.e., no measurable serum/urine M-protein) should be the only ones who are evaluated using FLC response criteria. The others should follow usual criteria and ignore FLC results*** with the exception of defining stringent complete response.

- **Evaluable disease:** Patients who do not have a “measurable” serum M-protein, serum free light chain, or urine M-protein.
- **Oligosecretory myeloma:** Patient with multiple myeloma who has NEVER had “measurable” serum M-protein or urine M-protein, but has had a detectable M-protein in his/her serum and/or urine and/or measurable serum free light chain.
- **Non-secretory myeloma:** Patient with multiple myeloma who has NEVER had a detectable M-protein in his/her serum and/or urine.

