15.1 Lenalidomide for Oral Administration (Revlimid®)

15.11 **Background:** Lenalidomide has antineoplastic, immunomodulatory and antiangiogenic characteristics via multiple mechanisms. Lenalidomide selectively inhibits secretion of proinflammatory cytokines (potent inhibitor of tumor necrosis factor-alpha secretion); enhances cell-mediated immunity by stimulating proliferation of anti-CD3 stimulated T cells (resulting in increased IL-2 and interferon gamma secretion); inhibits trophic signals to angiogenic factors in cells. Lenalidomide inhibits the growth of myeloma cells by inducing cell cycle arrest and cell death.

15.12 **Formulation and Dispensing:** Commercially available for oral administration as: Capsules: 5 mg, 10 mg, 15 mg and 25 mg

Lenalidomide is approved for marketing only under a FDA approved, restricted distribution program called RevAssist. Physicians, pharmacies, and patients must be registered; a maximum 28-day supply may be dispensed; a new prescription is required each time it is filled; pregnancy testing is required for females of childbearing potential.

15.13 **Preparation, storage, and stability:** Store oral capsules at controlled room temperature between 15°C and 30°C (59 °F and 86 °F). Refer to labeling on the bottle for expiration date of the commercial tablets.

15.14 **Administration:** Refer to the treatment section for specific administration instructions. Administer with water. Swallow capsule whole; do not break, open, or chew.

15.15 **Pharmacokinetic information:**
Absorption: Rapid
Metabolism: Approximately two-thirds of Lenalidomide is eliminated unchanged through urinary excretion.
Protein binding: ~30%
Time to peak, plasma: Healthy volunteers: 0.6-1.5 hours; Myeloma patients: 0.5-4 hours
Half-life elimination: ~3 hours
Excretion: Urine (~67% as unchanged drug)

15.16 **Potential Drug Interactions:**
Increased Effect/Toxicity: Abatacept and Anakinra may increase the risk of serious infection when used in combination with Lenalidomide. Lenalidomide may increase the risk of infections associated with vaccines (live organism).
Decreased Effect: Lenalidomide may decrease the effect of vaccines (dead organisms).
Herb/Nutraceutical Interactions: Avoid echinacea (has immunostimulant properties; consider therapy modifications).

15.17 **Known potential adverse events:** Consult the package insert for the most current and complete information.

Boxed Warnings:

1. Potential for human birth defects

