a) Absorption – oral absorption has been moderately rapid with first dose C_{max} occurring in 1.5 to 4 hrs. More than 70% of the pomalidomide dose is absorbed

in humans. A high fat meal decreased the rate of absorption but had minimal effect on overall extent of absorption; therefore drug may be administered without regard to food intake.

b) Distribution – Apparent volume of distribution in healthy subjects ranged from 74-138 L across a dose range of 1 to 10 mg daily.

Pomalidomide protein binding in human plasma is low to moderate (15.8% for R-enantiomer, 42.2% for S-enantiomer) and the binding is concentration independent in the concentration range of 30 and 1000 ng/mL. Drug distributes into semen.

c) Metabolism – Eight metabolites were detected in plasma, each at exposures < 10% of the plasma pomalidomide. CYP-dependent metabolites accounted for approximately 43% of the excreted radioactivity, while non-CYP dependent hydrolytic metabolites accounted for 25%, and excretion of unchanged pomalidomide accounted for 10%.

d) Excretion – In healthy patients, 72.8% of the dose was recovered in urine and 15.5% was recovered in feces. Less than 3% of the dose is excreted as unchanged pomalidomide in the urine. The geometric mean terminal elimination half-life ($t_{1/2}$) of pomalidomide was approximately 7.5 hours.

In pomalidomide renal studies, no dose adjustment was required for subjects with renal impairment. On hemodialysis days, subjects were instructed to take pomalidomide following hemodialysis. No dose adjustment of pomalidomide is required for patients with hepatic impairment as defined by the Child-Pugh criteria.

15.26 Potential Drug Interactions: Pomalidomide is partially metabolized by CYP1A2 and CYP3A4/5. Pomalidomide is also a substrate for P-glycoprotein (P-gp). Coadministration of pomalidomide with the strong CYP3A4/5 and P-gp inhibitor ketoconazole, or the strong CYP3A4/5 inducer carbamazepine, had no clinically relevant effect on exposure to pomalidomide. Coadministration of the strong CYP1A2 inhibitor fluvoxamine with pomalidomide increased mean exposure to pomalidomide by 125% compared to pomalidomide alone. If strong inhibitors of CYP1A2 are coadministered with pomalidomide, the pomalidomide dose should be reduced 50%.

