16.32 Secondary Outcome Analyses

16.321 Biomarkers and RR will be analyzed using logistic regressions to identify predictive biomarkers.

16.322 RR among African American (AA) patients and white MM patients will be evaluated after one cycle of treatment. Chi-Square (or Fischer Exact) test and 95% confidence intervals will be estimated to compared AA and white patients descriptively.

16.323 Correlation between the depth of hematological responses and biomarkers will be estimated. Logistic regressions and chi square (or Fischer exact) testing will be utilized.

16.33 Data & Safety Monitoring:

The principal investigator(s) and the study statistician will review the study at least twice a year to identify accrual, adverse event, and any endpoint problems that might be developing. The Mayo Clinic Cancer Center (MCCC) Data Safety Monitoring Board (DSMB) is responsible for reviewing accrual and safety data for this trial at least twice a year, based on reports provided by the MCCC Statistical Office.

Adverse Event Stopping Rules: (Each cohort will be analyzed separately) The stopping rules specified below are based on the knowledge available at study development. We note that the Adverse Event Stopping Rule may be adjusted in the event of either (1) the study re-opening to accrual or (2) at any time during the conduct of the trial and in consideration of newly acquired information regarding the adverse event profile of the treatment(s) under investigation. The study team may choose to suspend accrual because of unexpected adverse event profiles that have not crossed the specified rule below.

Accrual will be temporarily suspended to this study if at any time we observe events considered at least possibly related to study treatment (i.e. an adverse

event with attribute specified as “possible”, “probable”, or “definite”) that satisfy either of the following:

- If 3 or more out of the first 10 treated patients experience grade 4+ non-hematological toxicities
- If after the first 10 patients have been treated, 30% of patients experience grade 4+ non-hematologic toxicities

We note that we will review grade 5 adverse events deemed “unrelated” or “unlikely to be related”, to verify their attribution and to monitor the emergence of a previously unrecognized treatment-related adverse event.

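### In lenalidomide-treated patients, creatinine clearance sets the cycle-1 dose and may also move plasma markers, so the 16.321 and 16.323 biomarker models need a clearance-adjusted sensitivity analysis

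*Combined protocol and SAP*

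**What the plan says.** - **Dose rule.** In all four cohorts the cycle-1 lenalidomide dose depends on clearance. The footnote for cohorts C and D reads "Starting dose will be determined as per the creatinine clearance below (see 7.12", and the table for A and B carries the equivalent note. Section 7.12 gives "25 mg No adjustment required" above 60 ml/min and "10 mg once daily (may increase to 15 mg once daily after 2 cycles if nonresponsive but tolerating treatment" at 30-60. Any increase to 15 mg therefore comes after the cycle-1 endpoint.
- **Eligibility.** Section 3.17 requires "Calculated creatinine clearance ≥ 45 ml/min using the Cockcroft-Gault formula below". Among eligible patients the 10 mg stratum is thus 45-60 ml/min.
- **Markers.** Section 14.3 plans an untargeted metabolite screen of marrow and blood plasma, comparing responders with non-responders.
- **Model.** Section 16.321 says "Biomarkers and RR will be analyzed using logistic regressions to identify predictive biomarkers". Section 16.323 adds logistic regression and chi-square or exact tests against depth of response. Neither names a covariate, a stratum or a dose term. Clearance and starting dose are also absent from the grouping factor (5.1) and the descriptive factors (12.1-12.3).
- **Kidney function and analytes.** Section 11.1 says "the FLC levels vary considerably with changes in renal function". The documents make no such statement about metabolites.
- **Drug handling.** For lenalidomide, Section 15.15 says "Approximately two-thirds of Lenalidomide is eliminated unchanged through urinary excretion". For pomalidomide, Section 15.25 says "In pomalidomide renal studies, no dose adjustment was required for subjects with renal impairment".

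**The concern.** In lenalidomide-treated patients clearance determines the milligrams given in the one cycle on which response is judged. If it also influences the plasma level of a candidate marker, it is a possible common cause of marker and outcome. A model containing only the marker cannot then separate sensitivity to the drug from kidney function, and that separation is the aim of secondary goals 1 and 3.

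An untargeted screen makes this worse. Metabolites cleared by the kidney would tend to move together, so a cluster of hits could look like corroboration. Section 16.2 says the results will be used to judge whether further studies are warranted, so a follow-up study could be built on a proxy for renal function.

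**Working it through.** **1. The plan's own figures.** Accrual reproduces: 2 x (30 + 2) + 2 x (60 + 3) = 64 + 126 = 190. The evaluable cohort sizes used below are 30 (A, B) and 60 (C, D), 180 in all. The plan states no alpha, power or effect size for the biomarker models, so there is nothing further to reproduce. A two-sided 0.05 level is my yardstick.

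**2. Dose contrast.** 25 / 10 = 2.5, in milligrams. This is not an exposure ratio (see the objection).

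**3. Inputs the documents do not give (assumed).** These are the share of patients at or below 60 ml/min, the response rate in each stratum, and the correlation between metabolite and clearance.

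**4. Simulation.** Clearance is a standard normal variable g, and the low stratum is its lowest fraction f. The metabolite is m = -r x g + sqrt(1 - r^2) x noise. Response depends on the stratum only, never on m. The likelihood-ratio test of m is run without and then with clearance in the model. With 2,000 runs per setting, the simulation standard error near 5% is sqrt(0.05 x 0.95 / 2000) = 0.5 percentage points.

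*First set of assumptions:* f = 30%, everyone on lenalidomide, response 40% above 60 ml/min and 10-30% at or below, r = 0.5-0.8.

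| n | Null metabolite significant, unadjusted | With clearance in the model |
|---|---|---|
| 30 | about 6-16% | about 5-8% |
| 60 | about 7-31% | about 5-8% |

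The top of each range needs 10% v 40% and r = 0.8. In the mildest n=60 setting (30% v 40%, r = 0.5) repeat runs gave between 5.6% and about 8%, which is hardly distinguishable from the adjusted figure.

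*Second set:* f = 30%, r = 0.7, response 50% above 60 ml/min; the adjusted model contains the dose stratum. Cells show unadjusted / adjusted.

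| n | 50% v 50% | 50% v 35% | 50% v 20% |
|---|---|---|---|
| 30 | 5.8% / 6.0% | 7.2% / 6.2% | 15.2% / 7.0% |
| 60 | 5.8% / 5.7% | 8.2% / 6.0% | 22.4% / 5.2% |
| 180 (all cohorts pooled) | 5.5% / 5.6% | 17.2% / 5.2% | 51.6% / 5.8% |

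With f = 15%, r = 0.7 and 50% v 20%, the unadjusted figures are 9.4%, 12.4% and 27.7% for n = 30, 60 and 180. Section 16.31 keeps cohorts separate for the primary outcome; Section 16.32 does not say whether the biomarker models pool them. The pooled row also assumes that nobody takes pomalidomide.

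**5. Dilution.** Take the worst n=60 case of the first set (10% v 40%, r = 0.8). If half the patients take pomalidomide, or if only 10% have low clearance, it falls to about 10-12%. With both it is 5.6%.

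**6. Price of adjustment.** The variance inflation for the marker is 1 / (1 - r^2): 1 / (1 - 0.64) = 2.8 at r = 0.8, and 1 / (1 - 0.25) = 1.3 at r = 0.5. For a true marker (log-odds 0.8 per SD, no dose effect), adding clearance changes power as follows.

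| n | r = 0.5 | r = 0.8 |
|---|---|---|
| 30 | 51% to 42% | 53% to 24% |
| 60 | 83% to 70% | 81% to 41% |

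**The case against.** The case against is substantial, and most of it limits the point without removing it.

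- **Exposure.** A reader might infer that low-clearance patients receive 2.5 times less effective treatment, so that a null metabolite will be associated with response. The documents do not support this. About two-thirds of lenalidomide leaves unchanged in urine, so the lower dose may partly equalise exposure, and no response rate by dose or clearance is given. The bias is conditional on response differing by stratum for some reason. This stands.
- **Metabolites.** The statement about renal function concerns free light chains only. Its extension to metabolites is an assumption. Nor is FLC a clear second route: Section 11.1 limits FLC-based response to patients without measurable serum or urine M-protein and has both light chains considered. This stands.
- **Who is affected.** Pomalidomide is an option in C and D and needs no renal adjustment. Cohort A excludes renal insufficiency, so low-clearance patients may be few there. Both shrink the effect, as step 5 shows.
- **Reach.** Section 14.4 also plans genomics, transcriptomics and intracellular metabolomics of myeloma cells, which the plasma-clearance argument does not reach directly. The fix should be confined to plasma markers.
- **Pilot status.** The plan favours estimation over testing and sets no alpha, and 16.321 neither lists nor excludes covariates. That weakens the false-positive rate as a yardstick. It does not cure the problem, because a confounded odds ratio is biased as an estimate too.
- **Other imbalances.** The choice of IMiD and physician-determined dexamethasone are also unadjusted. Clearance is not the only candidate, but it is the one tied by rule to dose and plausibly to the marker.

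**Conclusion.** The point holds as a possibility, limited to plasma markers in lenalidomide-treated patients. The documents establish that clearance sets the cycle-1 dose, that eligible patients can fall on both sides of 60 ml/min, and that the biomarker models use neither clearance nor dose. They do not establish that response differs by stratum or that metabolites follow clearance.

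The size rests wholly on assumed inputs. It runs from no inflation (equal response in the strata), through barely visible (30% v 40%), to about 16% at n=30 and 31% at n=60 in the most unfavourable corner.

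A reader might also infer that clearance must enter the main model. The power loss in step 6 argues against that in a discovery pilot: strict adjustment could discard true markers. A sensitivity analysis shown beside the unadjusted estimate is the proportionate answer.

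**What to change.** In Sections 16.321 and 16.323, for the plasma markers of Section 14.3 in lenalidomide-treated patients:

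1. Keep the unadjusted estimate. Prespecify beside it a sensitivity analysis with baseline creatinine clearance as a continuous covariate, using the value that set the starting dose.
2. Repeat the analysis in patients above 60 ml/min, who share one protocol starting dose.
3. Describe a marker as a candidate predictor of IMiD response only with both results shown.
4. Report lenalidomide starting dose and IMiD received with each cohort's response rate.
5. State whether the biomarker models are fitted by cohort or pooled, since the possible bias is largest when pooled.

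The cost is analysis-plan wording and a few extra models. Clearance is already calculated for eligibility. The added estimates will be less precise: adjustment can roughly halve power for a marker strongly correlated with clearance. If 30% are at or below 60 ml/min and all take lenalidomide, the restricted analysis keeps 0.7 x 60 = 42 or 0.7 x 30 = 21 patients. Nothing here bears on the dose rule itself.
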